8. FIGURE OUTPUT CONVENTIONS

- Figures should be provided in RTF files using the SAS Output Delivery System (ODS), as Computer Graphics Metafile (CGM) formatted graphical output generated by SAS.
- The CGM file itself should contain the title or footer.
- The image should be clear and of high quality when viewed in the Word document, and when printed.
- In general, boxes around the figures should be used.

9. FOOTNOTE INFORMATION

Footers should be defined as follows:

- A continuous line of underscores ('_') will follow the body of the table or listing prior to any footnotes at the bottom of the page
- Footnotes will only appear on the last page of the output.
- Table footnotes should be defined using compute statements in the proc report, and should appear directly after the body of the table.
- The program path and name and version number (if applicable) should appear as footnote 1 at the bottom of the page
- The date/time stamp should appear as footnote 2 at the bottom of the page

Document: K:\DSP\SM-13496\KVA95374\Biostatistics\Documentation\SAP

Author: [REDACTED]

Version Number:

1.0

Version Date:

30MAR2017

Template No: CS_TP_BS016 – Revision 3

Reference: CS_WI_BS005

Effective Date: 01May2012

Copyright © 2012 [REDACTED] All rights reserved.

The contents of this document are confidential and proprietary to [REDACTED] reproduction is strictly prohibited.

[REDACTED] Unauthorized use, disclosure or

- Footnotes should be left-aligned.
- Footnotes should be in sentence case.
- Superscripts are used for footnotes linking to the body of the table.
- The choice of footnote symbols should be consistent. E.g. if you have the footnote “# indicates last observation carried forward” for one table, the same symbol and footnote should indicate LOCF for all tables.
- If text wraps across more than one line (for a note), the first letter for all lines of text after the first one will be indented to align beneath the first letter of the text in the first line.
- The page identification in the format Page X of Y (where Y is the total number of pages for the output) will appear at the top of the page, right aligned
- Common notes from table to table should appear in the same order.
- The symbols should appear in the same order as what they are defined in the table or listing, from left to right.

10. PROGRAMMING INSTRUCTIONS

Programming instructions must appear in blue font at the end of each table or listing shell. Programming instructions, where necessary, should follow the table or listing shells in blue font, beginning with the words “Programming Note” followed by a colon. These include notes on the output, reminders of how to handle missing values, repeat shells for similar tables etc.

DATES & TIMES

Depending on data available, dates and times will take the form yyyy-mm-ddThh:mm:ss.

SPELLING FORMAT

English US

PRESENTATION OF TREATMENT GROUPS

For outputs, treatment groups will be represented as follows and in that order:

Treatment Group	For Tables and Graphs	For Listings (include if different to tables)
Placebo	Placebo	Placebo

Document: K:\DSP\SM-13496\KVA95374\Biostatistics\Documentation\SAP

Author: [REDACTED]

Version Number:

1.0

Version Date:

30MAR2017

Template No: CS_TP_BS016 – Revision 3

Reference: CS_WI_BS005

Effective Date: 01May2012

Copyright © 2012 [REDACTED]. All rights reserved.

The contents of this document are confidential and proprietary to [REDACTED].
reproduction is strictly prohibited.

Unauthorized use, disclosure or

Treatment Group	For Tables and Graphs	For Listings (include if different to tables)
SM-13496 20-60mg	SM-13496 20-60mg	SM-13496 20-60mg
SM-13496 80-120mg	SM-13496 80-120mg	SM-13496 80-120mg
Combined SM-13496	Combined SM-13496	-
Screen Failure	-	Not Randomized

PRESENTATION OF VISITS

For outputs, visits will be represented as follows and in that order:

Long Name (default)	Short Name
Screening	Scr
Baseline	BL
Week 1	W1
Week 2	W2
Week 3	W3
Week 4	W4
Week 5	W5
Week 6	W6
Week 6 (LOCF)	W6LOCF

LISTINGS

All listings will be ordered by the following (unless otherwise indicated in the template):

- randomized treatment group (or treatment received if it's a safety output), first by active dose [by ascending dose group] and then control/ placebo
- center-subject ID,
- visit (where applicable),
- date (where applicable),
- For listings where non-randomized patients are included, these will appear in a category after the randomized treatment groups labeled 'Not Randomized'.

Document: K:\DSP\SM-13496\KVA95374\Biostatistics\Documentation\SAP
 Author: [REDACTED] Version Number: 1.0
 Version Date: 30MAR2017

Template No: CS_TP_BS016 – Revision 3
 Effective Date: 01May2012

Reference: CS_WI_BS005

Copyright © 2012 [REDACTED] All rights reserved. [REDACTED] Unauthorized use, disclosure or reproduction is strictly prohibited.

APPENDIX 2. PARTIAL DATE CONVENTIONS

Imputed dates will NOT be presented in the listings.

ALGORITHMS OF PARTIAL DATES FOR AEs AND MEDICATIONS

Partial dates for AEs and medications will be imputed as follows:

Adverse event or prior/concomitant medication start date (references to year and month refer to the year and month of the start date, respectively):

1. If year and month are known, and it is the month of the first dose date and the stop date is prior to the first dose date, use the first day of the month.
2. If year and month are known, and it is the month of the first dose date and the stop date is the same as or later than the first dose date, use the first dose date.
3. If year and month are known, and it is the month following the first dose date, use the first day of the month.
4. If year and month are known and it is any month prior to first dose date, use the first day of the month.
5. If only year is known, and it is previous to the year of the first dose date, use June 30th of that year. If it is the same as first dose date year, assume it is the first dose date. If it is later than the first dose date year, assume it is the first day of the year.
6. If the start date is completely missing, use the first dose date.
7. Should any of the previous start dates created be after a complete stop date provided, use the stop date instead of the date that would otherwise be created.
8. Otherwise, if start date is unknown leave as missing.

Adverse event or prior/concomitant medication stop date (references to year and month refer to the year and month of the stop date, respectively):

1. If year and month are known and study medication stopped during that month, use the stop date of study medication.
2. If year and month are known and study medication stopped after that month, use the last day of the month.
3. If year and month are known and study medication stopped prior to that month, use the first day of the month.
4. If only year is known, and it is the same as last dose date year, assume it is the last dose date. If it precedes the last dose date year, assume it is the last day of the year. If it is later than the last dose date year, assume it is the first day of the year.
5. If stop date is unknown and continuing is checked, set to date of last double-blind dose.
6. Should any of the previous stop dates created come before a start date, either a complete date or an imputed one, use the start date instead of the date that would otherwise be created.
7. Otherwise, if stop date is unknown leave as missing.

Document: K:\DSP\SM-13496\KVA95374\Biostatistics\Documentation\SAP
Author: [REDACTED] Version Number: 1.0
Version Date: 30MAR2017

Template No: CS_TP_BS016 -- Revision 3
Effective Date: 01May2012

Reference: CS_WI_BS005

Copyright © 2012 [REDACTED]. All rights reserved.
The contents of this document are confidential and proprietary to [REDACTED]. Unauthorized use, disclosure or reproduction is strictly prohibited.

ALGORITHM FOR PARTIAL DATES IN MEDICAL HISTORY

Partial dates for medical history (including psychiatric history) will be imputed as follows:

Medical history start date (references to year and month refer to the year and month of the start date, respectively):

1. If year and month are known, and it is the year or month previous to Screening, use the last day of the month.
2. If year and month are known, and it is the month of Screening, use Screening date – 1.
3. If only year is known, and it is previous to the year of Screening, use June 30th of that year.
4. If only year is known, and it is the year of Screening, use Screening date – 1.

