12. CONCOMITANT MEDICATIONS

Concomitant Medications will be presented for the Safety population and coded using **WHO Drug Dictionary Enhanced /WHO Herbal Dictionary v01DEC2013**.

ATC coding will be performed for the study, including screen failed patients. Medications will be summarized using ATC level 3 coding and Preferred Term.

See Appendix 2 for handling of partial dates for medications, in the case where it is not possible to define a medication as prior, concomitant, or post treatment, the medication will be classified as both prior and concomitant.

- 'Prior' medications are medications which started prior to the first dose of study medication. If they are ongoing at start of dosing then the medication will be classified as both prior and concomitant.
- Concomitant' medications are medications which:

Document: K:\DSP\SM-13496\KVA95374\Biostatistics\Documentation\SAP
Author: [REDACTED] Version Number: 1.0
Version Date: 30MAR2017

Template No: CS_TP_BS016 – Revision 3
Effective Date: 01May2012

Reference: CS_WI_BS005

Copyright © 2012 [REDACTED] All rights reserved.
The contents of this document are confidential and proprietary to [REDACTED]. Unauthorized use, disclosure or reproduction is strictly prohibited.

- o started prior to, on or after the first dose of study medication and started no later than one day before the end of the double blind phase
- o AND ended on or after the date of first dose of study medication or were ongoing at the end of the study.
- 'Post' medications are medications which started on the same day, or after the end of study treatment for patients who are not continuing into the extension study. For patients continuing into the extension study, the medication should be captured in the extension study database.

A summary of patients with concomitant use of antiparkinson medication will be summarized by treatment group. An additional summary will be produced categorizing medication categories related to Anxiolytics and Hypnotics.

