16.1. ADVERSE EVENTS

Adverse Events (AEs) will be coded using Medical Dictionary for Regulatory Activities (MedDRA) central coding dictionary, Version 19.1.

Treatment-emergent adverse events (TEAEs) are defined as AEs with a start date on or after the date of first dose through 7 days after study drug discontinuation (14 days for serious adverse events and deaths) or through the last double-blind dose date for patients continuing into the extension study. All AEs with an onset date after the consent date for the extension study but prior to the first dose in the extension study will be summarized separately in the extension study. Adverse events and serious adverse events (SAEs) with completely missing onset dates will be summarized as treatment emergent regardless of severity or relationship to study medication, unless the AE stop date occurs before the treatment start date.

See Appendix 2 for handling of partial dates for AEs. In the case where it is not possible to define an AE as treatment emergent or not, the AE will be classified by the worst case; i.e. treatment emergent.

An overall summary of patients within each of the categories described in the sub-section below, will be provided as specified in the templates.

Listings will include TEAEs and Non-TEAEs.

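### SAP Appendix 2 can date a drug or adverse event that ended before treatment to Day 1 when its start is missing or same-year year-only and its stop is partial

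*SAP*

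**What the plan says.** SAP Appendix 2 gives one ordered list of rules for start dates and one for stop dates. Both lists serve adverse events and medications.

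- Start rule 5, for a start with only the year known: "If it is the same as first dose date year, assume it is the first dose date".
- Start rule 6: "If the start date is completely missing, use the first dose date".
- Start rule 7, the correction for a start that falls after the stop: "Should any of the previous start dates created be after a complete stop date provided, use the stop date".
- Stop rule 2: "If year and month are known and study medication stopped after that month, use the last day of the month".
- Stop rule 4, for a stop with only the year known: "If it precedes the last dose date year, assume it is the last day of the year".
- Stop rule 6: "Should any of the previous stop dates created come before a start date, either a complete date or an imputed one"; in that case the stop is replaced by the start.

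The resulting dates feed two classifications. SAP 12 calls a medication concomitant if it began early enough and ended on or after first dose (or was still ongoing at the end), and prior if it began before first dose. For a drug ongoing when dosing begins, and also for one that cannot be placed, "the medication will be classified as both prior and concomitant". SAP 16.1 defines a TEAE by a start on or after first dose. It counts events with wholly missing onset as treatment-emergent "unless the AE stop date occurs before the treatment start date".

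**The concern.** The two correction rules are not symmetrical. Start rule 7 trusts the stop only if it is complete. Stop rule 6 trusts the start even if it is imputed. When the start is a Day 1 default and the stop is partial but certainly earlier, the default overrides the recorded information.

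The worst-case clauses in SAP 12 and 16.1 do not explain this, because they cover records that cannot be classified. A drug recorded as stopped in April, with first dose on 10 May, can be classified. Start rules 1 and 7 and the 16.1 exception all aim to keep such records out of the treatment period.

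Two related problems follow.

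- For adverse events with wholly missing onset, Appendix 2 and SAP 16.1 can give opposite answers, because 16.1 does not say whether it means the recorded or the imputed stop. Year-only onsets have no exception at all.
- A drug ongoing at first dose with a missing or same-year year-only start is dated Day 1. It then no longer began before first dose, so it drops out of the prior class, although SAP 12 wants it in both.

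At stake is the accuracy of the medication summaries and TEAE tables.

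**Working it through.** The plan has no figure to reproduce. The check applies the rules literally, in order.

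**Inputs.** The rules are those of SAP Appendix 2, with the definitions in SAP 12 and 16.1. The dates are assumed for illustration: first dose 10 May 2015 (Day 1), last dose 20 June 2015 (Day 42).

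**One record: start missing, stop April 2015.**
1. Start rule 6 gives start = 10 May 2015.
2. Start rule 7 does not apply, because the stop is not complete.
3. Stop rule 2 gives stop = 30 April 2015, since study drug stopped after April.
4. Stop rule 6 finds 30 April earlier than 10 May, so stop = 10 May 2015.
5. A drug that ends on 10 May is concomitant. An event that starts on 10 May is a TEAE.

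**The same record with a complete stop, 20 April 2015.** Start rule 6 gives 10 May and start rule 7 moves it to 20 April. The record stays before treatment. Losing only the day of the month reverses the classification, although both versions show that the record ended before first dose.

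**All illustrative pairs with both dates incomplete and a stop certainly before Day 1:**

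| Recorded start | Recorded stops tried | Pairs | Moved to Day 1 |
|---|---|---|---|
| missing | 2015-04, 2015-03, 2014-12, 2014 | 4 | 4 |
| 2015 | 2015-04, 2015-03 | 2 | 2 |
| 2014 | 2015-04, 2015-03, 2014-12, 2014 | 4 | 0 |
| 2015-03 | 2015-04, 2015-03 | 2 | 0 |
| 2015-04 | 2015-04 | 1 | 0 |
| 2014-11 | 2015-04, 2015-03, 2014-12, 2014 | 4 | 0 |
| Total | | 17 | 6 |

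The fault therefore needs a start that is missing or year-only in the first-dose year, together with a partial stop wholly before first dose. The 6 of 17 describes these chosen pairs and is not an expected rate.

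**How often the conditions could arise.** Protocol 5.3 records medications from Visit 1, and Protocol 6.4.1.3 collects adverse events from consent. Visit 1 falls on Day -14 to Day -3. In the example, Day -14 is 26 April, so of the six moved pairs only the two with an April stop fit that window. For a month-only stop, screening must cross a month boundary. With first-dose days spread evenly over the year and screening k days earlier, the share that crosses is 12k/365:

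- k = 3: 36/365 = 10%
- k = 7: 84/365 = 23%
- k = 14: 168/365 = 46%

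These shares are ceilings on where the fault is possible under those collection windows. Both dates must also be incomplete in the way described, and the documents give no rate for that.

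**Check of the correction.** Capping the imputed start at the latest date the recorded stop allows gives 30 April, 31 March or 31 December for the six pairs. None is then concomitant or a TEAE. The other 11 pairs do not change.

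**The case against.** The strongest reply is that this will rarely happen and is partly covered already.

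- **Rarity.** Psychotropics are withdrawn during a supervised screening phase. The eCRF has a stop-date field, and missing data are queried with the investigator (Protocol 5.3.2.1, 5.3 and 8.5.1). An unknown start does no harm if the stop is complete. This stands, and it limits the size of the problem.
- **Adverse events.** Read on the recorded stop, the exception in SAP 16.1 keeps an event with wholly missing onset out of the TEAE tables. This stands as one reading, but the text does not choose it, and same-year year-only onsets are not covered.
- **Prior medications.** The SAP 12 clause for unclassifiable drugs can be read to cover an ongoing drug with unknown start, and a drug with an earlier year recorded gets 30 June of that year and stays prior. Both points stand. However, SAP 12 sends the reader to Appendix 2 first, and after imputation nothing looks unclassifiable.

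A reader might go further and infer that patients with a washed-out psychotropic are wrongly removed from the per-protocol set. The documents do not support that as a fact. SAP 5.2 says that the first three per-protocol conditions are checked by program; the psychotropic condition is the fourth and goes through medical review. Nothing says that imputed dates decide what counts as use during treatment. The review sheet does feed the derived datasets, so a false flag remains possible.

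**Conclusion.** The rules as written give a wrong classification for a definable, narrow set of records: start missing or year-only in the first-dose year, with a partial stop that excludes Day 1. This follows from literal application in the stated order and needs no assumption about the data. The conflict with SAP 16.1 for wholly missing onsets depends on which stop that section means, and the text leaves this open. The awkward fit with SAP 12 for drugs ongoing at first dose is a lesser inconsistency of the same origin.

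The number of records affected cannot be estimated from the documents and is probably small. The effect is on medication and TEAE tables. Per-protocol membership could be touched only if imputed dates were used in deciding it, which the SAP does not state, so no count of lost patients can be given. The primary MMRM in the ITT population is unaffected. This is a minor correction worth making.

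**What to change.** Make three wording changes.

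1. Extend start rule 7 to partial stops. If the latest date that the recorded stop allows (last day of the month, or 31 December for a year-only stop) is before first dose, a start imputed under rule 5 or 6 is set no later than that date.
2. State in SAP 16.1 that the exception for missing onset is judged on the recorded stop, including a partial one.
3. State in SAP 12 that a drug ongoing at first dose with a missing or same-year year-only start is classed as both prior and concomitant.

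Leave stop rule 6 otherwise unchanged. Restricting it to complete starts, and moving imputed starts back instead, would create a new error. Take a drug recorded as started in July 2015 and continuing, with last dose on 20 June. If start rule 3 is read as covering any later month, the start is 1 July. Stop rule 5 gives 20 June, and stop rule 6 now corrects that to 1 July. Moving the start back to 20 June would contradict the recorded month and place a post-treatment record on treatment.

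The cost is a few sentences and a small program change, with no new data.

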APPENDIX 3. SAS CODE

Treatment: TRTPN
Analysis visit: AVISIT

1. Mixed Model Repeated Measures (MMRM) Analysis

Note: Ensure that input dataset is sorted by USUBJID AVISIT prior to initiating the MIXED procedure.

```
ods output estimates=outset /*Output from estimate statement*/  
diffs=outdiff /*Treatment Group Comparison*/  
R=outr /*R matrix */  
lsmeans=outlsmean; /*LSmeans of each treatment group*/
```

```
PROC MIXED;  
CLASS SUBJID POOLSITE TRTPN AVISIT;  
MODEL CFB = BASE POOLSITE TRTPN AVISIT TRTPN*AVISIT/DDFM=KR;  
REPEATED AVISIT /TYPE=UN SUBJECT=SUBJID R;  
LSMEANS TRTPN* AVISIT /PDIFF CL;  
ESTIMATE 'LINEAR TREND TEST FOR DOSE RESPONSE'  
TRTPN 0 1 -1 TRTPN*AVISIT 0 0 0 0 0 0 0 0 0 0 0 0 0 1  
0 0 0 0 0 0 -1/CL;  
ESTIMATE 'DOSE-RESPONSE 20-60 vs 80-120' TRTPN -1 1 0 TRTPN*AVISIT  
0 0 0 0 0 0 -1 0 0 0 0 0 0 1 0 0 0 0 0 0 0/CL;  
RUN;
```

a. Mixed Model Repeated Measures (MMRM) Analysis for the case above
model fails to converge

```
PROC MIXED empirical;
```

Document:	K:\DSP\SM-13496\KVA95374\Biostatistics\Documentation\SAP	Version Number:	1.0
Author:	[REDACTED]	Version Date:	30MAR2017

Template No: CS_TP_BS016 – Revision 3
Effective Date: 01May2012

Reference: CS_WI_BS005

Copyright © 2012 [REDACTED] All rights reserved.
The contents of this document are confidential and proprietary to [REDACTED]. Unauthorized use, disclosure or reproduction is strictly prohibited.

```
CLASS SUBJID POOLSITE TRTPN AVISIT;  
MODEL TOTCFB = TOTBL POOLSITE TRTPN AVISIT TRTPN*AVISIT;  
REPEATED AVISIT /TYPE=XXX SUBJECT=SUBJID R;  
LSMEANS TRTPN*AVISIT /PDIFF CL;  
ESTIMATE 'LINEAR TREND TEST FOR DOSE RESPONSE'  
TRTPN 0 1 -1 TRTPN*AVISIT 0 0 0 0 0 0 0 0 0 0 0 0 1  
0 0 0 0 0 0 -1/CL;  
ESTIMATE 'DOSE-RESPONSE 20 vs 80-160' TRTPN -1 1 0 TRTPN*  
AVISIT 0 0 0 0 0 0 -1 0 0 0 0 0 0 1 0 0 0 0 0 0/CL;  
RUN;
```

XXX: application order
Heterogeneous Toeplitz (TYPE=TOEPH)
Heterogeneous first-order autoregressive (TYPE=ARH(1))
Toeplitz (TYPE=TOEP)

2. Analysis of Covariance

```
PROC MIXED;  
CLASS TRTPN POOLSITE;  
MODEL CFB = TRTPN POOLSITE BASE;  
LSMEANS TRTPN / PDIFF CL;  
ESTIMATE 'LINEAR TREND' TRTPN 0 1 -1 /CL;  
ESTIMATE 'DOSE-RESPONSE 20 vs 80-160' TRTPN -1 1 0/CL;  
RUN;
```

3. Sensitivity Analysis

a. Random Effects Pattern Model

```
If TRT01PN=1 then DOSE1=1 else DOSE1=0;  
If TRT01PN=2 then DOSE2=1 else DOSE2=0;  
If COMPLFL="Y" then DROP=1 else DROP=0;
```

```
PROC MIXED;  
CLASS USUBJID;  
MODEL AVAL = QSDAY DOSE1 DOSE2 QSDAY*DOSE1 QSDAY*DOSE2  
DROP DROP*QSDAY DROP*DOSE1 DROP*DOSE2  
DROP*DOSE1*QSDAY DROP*DOSE2*QSDAY / SOLUTION COVB  
DDFM=KR;  
RANDOM INTERCEPT DAY/SUB=USUBKID TYPE=UN G;  
RUN;
```

```
PROC IML;  
USE VCOV1;  
READ all into vcovm;  
USE estb;  
READ all into estbm;
```

```
MEANV = ESTBM[,1];
```

Document: K:\DSP\SM-13496\KVA95374\Biostatistics\Documentation\SAP

Author: [REDACTED]

Version Number:

1.0

Version Date:

30MAR2017

Template No: CS_TP_BS016 - Revision 3

Reference: CS_WI_BS005

Effective Date: 01May2012

Copyright © 2012 [REDACTED] All rights reserved

The contents of this document are confidential and proprietary to [REDACTED]
reproduction is strictly prohibited.

Unauthorized use, disclosure or

```
VARB = VCOVM[1:12,1:12];
A = { 1 0 0 0 0 0 0 0 0 0 0 0, /* Completer - control intercept */
      0 1 0 0 0 0 0 0 0 0 0 0, /* Completer - control slope */
      0 0 1 0 0 0 0 0 0 0 0 0, /* Completer - dose1 intercept diff */
      0 0 0 1 0 0 0 0 0 0 0 0, /* Completer - dose2 intercept diff */
      0 0 0 0 1 0 0 0 0 0 0 0, /* Completer - dose1 slope diff */
      0 0 0 0 0 1 0 0 0 0 0 0, /* Completer - dose2 slope diff */

      1 0 0 0 0 0 1 0 0 0 0 0, /* Dropout - control intercept */
      0 1 0 0 0 0 0 1 0 0 0 0, /* Dropout - control slope */
      0 0 1 0 0 0 0 0 1 0 0 0, /* Dropout - dose1 intercept diff */
      0 0 0 1 0 0 0 0 0 1 0 0, /* Dropout - dose2 intercept diff */
      0 0 0 0 1 0 0 0 0 0 1 0, /* Dropout - dose1 slope diff */
      0 0 0 0 0 1 0 0 0 0 0 1 }; /* Dropout - dose2 slope diff */

meancd = A*meanv;
varccd = A*varb*T(A);

*COMPLETERS;
meanc = meancd[1:6,];
serrc = sqrt(vecdiag(varccd[1:6,1:6]));
zvalc = meanc/serrc;
lowec=meanc-1.96*serrc;
uppec=meanc+1.96*serrc;
probc = 2*(1-PROBNORM(abs(zvalc)));

**DROPOUTS;
meand = meancd[7:12,];
serrd = sqrt(vecdiag(varccd[7:12,7:12]));
zvald = meand/serrd;
lowed=meand-1.96*serrd;
upped=meand+1.96*serrd;
probd = 2*(1-PROBNORM(abs(zvald)));

/* indicator matrix to average over 2 patterns */
B = { 1 0 0 0 0 0 1 0 0 0 0 0,
      0 1 0 0 0 0 0 1 0 0 0 0,
      0 0 1 0 0 0 0 0 1 0 0 0,
      0 0 0 1 0 0 0 0 0 1 0 0,
      0 0 0 0 1 0 0 0 0 0 1 0,
      0 0 0 0 0 1 0 0 0 0 0 1 };

/* derivative matrix for average with respect to proportion
   (for application of delta method) */
C = { 1 0 0 0 0 0 -1 0 0 0 0 0,
      0 1 0 0 0 0 0 -1 0 0 0 0,
      0 0 1 0 0 0 0 0 -1 0 0 0,
      0 0 0 1 0 0 0 0 0 -1 0 0,
      0 0 0 0 1 0 0 0 0 0 -1 0,
      0 0 0 0 0 1 0 0 0 0 0 -1 };

propcd = J(12,12,0);
```

Document: K:\DSP\SM-13496\KVA95374\Biostatistics\Documentation\SAP
Author: [REDACTED] Version Number: 1.0
Version Date: 30MAR2017

Template No: CS_TP_BS016 – Revision 3 Reference: CS_WI_BS005
Effective Date: 01May2012

Copyright © 2012 [REDACTED] All rights reserved. [REDACTED] Unauthorized use, disclosure or reproduction is strictly prohibited.

```
propcd[1,1] = &grp11/(&grp11+&grp21); /* Completer - control intercept
*/
propcd[2,2] = &grp11/(&grp11+&grp21); /* Completer - control slope
*/
propcd[3,3] = &grp12/(&grp12+&grp22); /* Completer - dose1 intercept
diff */
propcd[4,4] = &grp13/(&grp13+&grp23); /* Completer - dose2 intercept
diff */
propcd[5,5] = &grp12/(&grp12+&grp22); /* Completer - dose1 slope
diff */
propcd[6,6] = &grp13/(&grp13+&grp23); /* Completer - dose2 slope
diff */

propcd[7,7] = &grp21/(&grp11+&grp21); /* Dropout - control
intercept */
propcd[8,8] = &grp21/(&grp11+&grp21); /* Dropout - control slope
*/
propcd[9,9] = &grp22/(&grp12+&grp22); /* Dropout - dose1
intercept diff */
propcd[10,10] = &grp23/(&grp13+&grp23); /* Dropout - dose2
intercept diff */
propcd[11,11] = &grp22/(&grp12+&grp22); /* Dropout - dose1 slope
diff */
propcd[12,12] = &grp23/(&grp13+&grp23); /* Dropout - dose2 slope
diff */

propcdd = J(6,6,0);
propcdd[1,1] = &grp11*&grp21/((&grp11+&grp21)**3);
propcdd[2,2] = &grp11*&grp21/((&grp11+&grp21)**3);
propcdd[3,3] = &grp12*&grp22/((&grp12+&grp22)**3);
propcdd[4,4] = &grp13*&grp23/((&grp13+&grp23)**3);
propcdd[5,5] = &grp12*&grp22/((&grp12+&grp22)**3);
propcdd[6,6] = &grp13*&grp23/((&grp13+&grp23)**3);

meanpm = B*propcd*meancd;
varcpm = B*propcd*varccd*propcd*T(B)
+ propcdd*C*meancd*T(meancd)*T(C);
serrpm = sqrt(vecdiag(varcpm));
zvalpm = meanpm/serrpm;
lowepm=meanpm-1.96*serrpm;
uppepm=meanpm+1.96*serrpm;
probp = 2*(1-PROBNORM(abs(zvalpm)));

CREATE outdata var {meanc serrc lowec uppec probc meand serrd lowed upped
probd meanpm serrpm lowepm uppepm probpm};
append;
close outdata;

QUIT;

*Model repeated without drop out pattern:

PROC MIXED;
CLASS USUBJID;
MODEL AVAL = QSDAY DOSE1 DOSE2 DAY*DOSE1 DAY*DOSE2 /
```

Document: K:\DSP\SM-13496\KVA95374\Biostatistics\Documentation\SAP

Author:

Version Number:

1.0

Version Date:

30MAR2017

Template No: CS_TP_BS016 - Revision 3

Reference: CS_WI_BS005

Effective Date: 01May2012

Copyright © 2012 All rights reserved.

The contents of this document are confidential and proprietary to

Unauthorized use, disclosure or reproduction is strictly prohibited.

SOLUTION COVB DDFM = KR;
RANDOM INTERCEPT DAY /SUB=USUBJID TYPE=UN G;
RUN;

b. Multiple Imputation

NOTE: Placebo based imputation

```
PROC MI
VAR SITEGR1N SCORE_1 SCORE_2 SCORE_3 SCORE_4 SCORE_5 SCORE_6
SCORE_7;
BY TRT01PN;
MCMC CHAIN=MULTIPLE IMPUTE=MONOTONE;
RUN;

%MACRO MI_IMP(INDATA=, ANVIS=, SEED=, VAR1=, VAR2=, OUTDATA=);
DATA EFF_MONO_IMP EFF_MONO_REST;
SET &INDATA;
IF TRT01PN IN (2,3) AND LASTVIS >=&ANVIS THEN OUTPUT
EFF_MONO_REST;
ELSE OUTPUT EFF_MONO_IMP;
RUN;

PROC SORT DATA= EFF_MONO_IMP;
BY _IMPUTATION_;
RUN;

PROC MI DATA=EFF_MONO_IMP OUT=EFF_REG_IMP NIMPUTE=1 SEED=&SEED
MINIMUM=0 MAXIMUM=60;
VAR &VAR1 &VAR2;
BY _IMPUTATION_;
MONOTONE REGRESSION(&VAR2= &VAR1 / DETAILS);
RUN;

DATA &OUTDATA;
SET EFF_MONO_REST EFF_REG_IMP;
RUN;

PROC DATASETS;
DELETE EFF_MONO_IMP EFF_MONO_REST EFF_REG_IMP;
RUN;
%MEND MI_IMP;
```

Document: K:\DSP\SM-13496\KVA95374\Biostatistics\Documentation\SAP
Author: [REDACTED] Version Number: 1.0
Version Date: 30MAR2017

Template No: CS_TP_BS016 – Revision 3
Effective Date: 01May2012

Reference: CS_WI_BS005

Copyright © 2012 [REDACTED] All rights reserved.
The contents of this document are confidential and proprietary to [REDACTED]. Unauthorized use, disclosure or reproduction is strictly prohibited.

```
%MI_IMP(INDATA=EFF_MONO, ANVIS=2, SEED=445566, VAR1=SCORE_1 SCORE_2,  
VAR2=SCORE_3, OUTDATA=EFF_IMP1);  
%MI_IMP(INDATA=EFF_IMP1, ANVIS=3, SEED=445566, VAR1=SCORE_1 SCORE_2  
SCORE_3, VAR2=SCORE_4, OUTDATA=EFF_IMP2);  
%MI_IMP(INDATA=EFF_IMP2, ANVIS=4, SEED=445566, VAR1=SCORE_1 SCORE_2  
SCORE_3 SCORE_4, VAR2=SCORE_5, OUTDATA=EFF_IMP3);  
%MI_IMP(INDATA=EFF_IMP3, ANVIS=5, SEED=445566, VAR1=SCORE_1 SCORE_2  
SCORE_3 SCORE_4 SCORE_5, VAR2=SCORE_6, OUTDATA=EFF_IMP4);  
%MI_IMP(INDATA=EFF_IMP4, ANVIS=6, SEED=445566, VAR1=SCORE_1 SCORE_2  
SCORE_3 SCORE_4 SCORE_5 SCORE_6, VAR2=SCORE_7, OUTDATA=EFF_IMP5);
```

```
DATA MI_EFF;  
  SET EFF_IMP5;  
  AVISITN=1;  
  DIFF=SCORE_2-SCORE_1;  
  OUTPUT;  
  AVISITN=2;  
  DIFF=SCORE_3-SCORE_1;  
  OUTPUT;  
  AVISITN=3;  
  DIFF=SCORE_4-SCORE_1;  
  OUTPUT;  
  AVISITN=4;  
  DIFF=SCORE_5-SCORE_1;  
  OUTPUT;  
  AVISITN=5;  
  DIFF=SCORE_6-SCORE_1;  
  OUTPUT;  
  AVISITN=6;  
  DIFF=SCORE_7-SCORE_1;  
  OUTPUT;
```

```
RUN;
```

```
ods listing close;
```

```
PROC MIXED;
```

```
  CLASS USUBJID TRT01PN AVISITN SITEGR1N;  
  MODEL      DIFF=SCORE_1      TRT01PN      AVISITN      SITEGR1N  
TR01PN*AVISITN/DDFM=KR SOLUTION CL;  
  REPEATED AVISITN /SUBJECT=USUBJID TYPE=UN;
```

Document:	K:\DSP\SM-13496\KVA95374\Biostatistics\Documentation\SAP	Version Number:	1.0
Author:	[REDACTED]	Version Date:	30MAR2017

Template No: CS_TP_BS016 – Revision 3
Effective Date: 01May2012

Reference: CS_WI_BS005

Copyright © 2012 [REDACTED] All rights reserved.
The contents of this document are confidential and proprietary to [REDACTED]
reproduction is strictly prohibited.

Unauthorized use, disclosure or

```
LSMEANS TRT01PN*AVISITN / DIFF=CONTROL("1", "6")diff=control("1"
"6") CL;
BY _imputation_;
RUN;
```

```
PROC MIANALYZE;
CLASS TRT01PN;
BY _TRT01PN;
MODELEFFECTS TRT01PN;
run;
```

```
proc mianalyze parms=ls_mean;
CLASS TRT01PN;
BY AVISITN;
MODELEFFECTS TRT01PN;
RUN;
```

4. MADRS 50% Responders Logistic Model

Note: Placebo will be reference

Note: All SM-13496 groups will be included in a model

```
PROC LOGISTIC DESCENDING;
CLASS TRTPN POOLSITE / PARAM=REF;
MODEL RESP50 = TRTPN POOLSITE BASE;
CONTRAST 'LUR 20-60 vs. PLACEBO' TRTPN 1 0/ESTIMATE=EXP;
CONTRAST 'LUR 80-120 vs. PLACEBO' TRTPN 0 1/ESTIMATE=EXP;
RUN;
```

5. Ranked ANCOVA (Selected Safety Parameters)

```
PROC RANK OUT= OUT1 NPLUS1 TIES = MEAN;
VAR VSCFB VSBASE;
RANKS RKVSCFB RKVSBASE;
RUN;
```

```
PROC GLM DATA = OUT1;
MODEL RKVSCFB = RKVSBASE;
OUTPUT OUT=RESIDUAL R=RESID;
RUN;
```

```
PROC FREQ DATA = RESIDUAL;
TABLES TRTPN*RESID / NOPRINT CMH2;
RUN;
```

6. NNT and 95% CI

Document: K:\DSP\SM-13496\KVA95374\Biostatistics\Documentation\SAP

Author: [REDACTED]

Version Number:

1.0

Version Date:

30MAR2017

Template No: CS_TP_BS016 – Revision 3

Reference: CS_WI_BS005

Effective Date: 01May2012

Copyright © 2012 [REDACTED] All rights reserved.

The contents of this document are confidential and proprietary to [REDACTED] reproduction is strictly prohibited.

[REDACTED] Unauthorized use, disclosure or

```
pi0a: responder rate of SM-13496 group
pi1: responder rate of placebo group
delta_ua : upper limit of NNT before taking the reciprocal
delta_la : lower limit of NNT before taking the reciprocal

nnt = round(1/(pi0a - pi1), 0.01);
delta_la = pi0a - pi1 - 1.96*sqrt(pi1*(1-pi1)/PCOUNT + pi0a*(1-
pi0a)/COUNT);
delta_ua = pi0a - pi1 + 1.96*sqrt(pi1*(1-pi1)/PCOUNT + pi0a*(1-
pi0a)/COUNT);

if pi0a>=pi1 then do;
    lower_ba = min(delta_ua, 1);
    upper_ba = max(delta_la, 0.000001);
end;
else if pi0a<pi1 then do;
    lower_ba = min(delta_ua, -0.000001);
    upper_ba = max(delta_la, -1);
end;

lcia = floor(round(1/lower_ba));
ucia = ceil(round(1/upper_ba));

* CA test */
Placebo group = 0
SM-13496 group = 1

ODS OUTPUT TrendTest=__TREND;
proc freq data=_madr;
    table TRTPN *resp50/cmh trend;
run;

/* Between group effect size */
data bes01 ;
    pi0a = COUNT/COUNT ; ***a = treatment 1***;
    pi1 = _PCOUNT/PCOUNT ; ***placebo***;
    rslt0a=2*(arcsin(sqrt(pi0a)));
    rslt1 =2*(arcsin(sqrt(pi1)));
    h = abs(rslt0a - rslt1) ;
    ch = put ( h , 5.2 );
run ;

7. Hochberg procedure

data a;
    input Test$ Raw_P @@;
    datalines;
test01 0.28282 test02 0.30688 test03 0.71022
```

Document: K:\DSP\SM-13496\KVA95374\Biostatistics\Documentation\SAP
Author: [REDACTED] Version Number: 1.0
Version Date: 30MAR2017

Template No: CS_TP_BS016 -- Revision 3
Effective Date: 01May2012

Reference: CS_WI_BS005

Copyright © 2012 [REDACTED] All rights reserved. [REDACTED]
The contents of this document are confidential and proprietary to [REDACTED]. Unauthorized use, disclosure or reproduction is strictly prohibited.

```

;
proc multtest inpvalues=a hoc;
run;

```

